9.4 Day 1 – Post-Infusion

The following procedures will be performed post-infusion on Day 1:

- Record any AEs that have occurred and any changes in concomitant medication since the infusion. Special attention should be paid to monitoring for AEs related to the central nervous system including tremors.
- Record vital signs ([semi]supine BP, heart rate, heart rhythm from ECG). Should be recorded before an electrical cardioversion, if applicable.
- Collect PK plasma samples at 45 min \pm 5 min, 1 h \pm 5 min, 1 h 30 min \pm 5 min, 4 h \pm 5 min, and 8 h \pm 5 min after start of infusion.
- Continue 12-lead Holter monitoring until after the 8 h PK sample is collected.
- Perform telemetry until at least 8h after infusion start.
- Do electrical cardioversion in case of AF persistence (refer to the Schedule of Assessments in [Section 8.1.2](#) for exact timing and parameters).

Prior to discharge of the patient, the Day 2 follow-up visit will be scheduled.

9.5 Day 2

The following procedures will be performed on Day 2:

- Record any AEs that have occurred since Day 1 and any changes in concomitant medication. Special attention should be paid to monitoring for AEs related to the central nervous system including tremors.
- Record vital signs (BP, heart rate, heart rhythm from ECG).
- Collect blood samples for clinical chemistry (refer to the Schedule of Assessments in [Section 8.1.2](#) for parameters included).
- Collect PK plasma samples 24 h ± 2 h after start of infusion.
- Perform a 12-lead ECG 24h ± 2 h after start of infusion.

The Day 30 follow-up visit will be scheduled.

9.6 Follow-up/Discontinuation Visit (Day 30)

The follow-up visit will take place 30 days ± 5 days after the previous visit. The following procedures will be performed at the follow-up visit (Day 30):

- Record any AEs that have occurred and any changes in concomitant medication since the previous visit.
- Perform a brief physical examination (general appearance, cardiovascular, respiratory, gastrointestinal, other).
- Record vital signs ([semi]supine BP, heart rate, heart rhythm from ECG).
- Collect blood samples for haematology and clinical chemistry (refer to the Schedule of Assessments in [Section 8.1.2](#) for parameters included), urea (BUN), and INR/APTT.
- Perform a 12-lead ECG.

9.7 Duration of Treatment

Study drug infusion is planned for 30 min for each patient.

Regardless of which study part (Part 1 or 2) the patient participates in, the overall study duration for each patient is up to a maximum of 42 days. The screening and randomisation will occur within 7 days (inclusive) from onset of AF. The duration of treatment and post-treatment follow-up will be 30 days ± 5 days from start of infusion to the follow-up visit.

10 EFFICACY, PHARMACOKINETICS, AND SAFETY VARIABLES

The planned schedule of assessments is shown in [Section 8.1.2](#). The schedule is same for both parts of the study (Parts 1 and 2).

10.1 Efficacy, Pharmacokinetics, and Safety Measurements

10.1.1 Efficacy Variables

10.1.1.1 Holter Recording

ECG assessments for primary efficacy endpoint will be based on Holter ECG. Conversion from AF will be determined by the investigator and documented with a rhythm strip confirming conversion; time of conversion will be recorded in minutes after start of infusion.

In addition, the Holter will record ECG continuously and detect conversion from AF as well as monitor sustainability of the rhythm after conversion. The 12-lead Holter monitoring equipment will be centrally provided by Clario. Analysis of the primary and secondary efficacy endpoints will be based on Holter ECG and ECGs collected by the site. The Holter ECG recording will be initiated 30 min before the planned start of study drug infusion and will be continued for at least 8 h until after the last PK sampling on Day 1. Records will be available for assessment by the DMC at the IAs, will be used for the analysis of the primary and secondary efficacy endpoints, and may be further used for retrospective safety analyses ([Section 10.1.3.5](#)).

The following measurements will be provided for all ECGs extracted from the Holter recording: RR, PR, QRS, QT, QTcF, QTcB (optional), heart rate, T- and U- wave morphology classifications.

Triplicate ECGs will be extracted at the same time points as PK sampling except the 24h PK sampling (see Schedule of Assessments in [Section 8.1.2](#)) and will be read in a semi-automated manner by a blinded cardiologist. The arithmetic mean of the replicate values was used as the value for that time point.

The ECG laboratory processes all ECGs to produce regulatory-ready research data with all ECG interval duration measurement quality control and quality assurance processes completed on a continuing basis according to ERT's quality assurance guidelines and standard operating procedures (SOPs).

Central reading in the ECG core laboratory adheres to the following principles:

- The actual times of dosing, extraction windows, and PK sampling are communicated to the central ECG laboratory by the site.

- The central ECG laboratory identifies periods of stable heart rate on the continuous 12-lead ECG tracing within the 3-minute extraction window.
- Review of ECGs from a particular patient is performed by a single reader.
- Baseline and on-treatment ECGs are based on the same lead ECGs from a single patient.
- The primary analysis lead is Lead II. If Lead II is not analysable, then primary lead of analysis is changed to another lead for the entire patient dataset.

Bedside safety ECGs will be collected by the site as described in [Section 10.1.3.5](#).

10.1.2 Pharmacokinetic Variables

10.1.2.1 Plasma Concentrations of AP30663

Venous blood samples for the determination of plasma concentrations of AP30663 will be collected at the times indicated in the Schedule of Assessments in [Section 8.1.2](#).

At each of the 11 (or 12 in case of conversion from AF) sampling time points for PK assessment, 4 mL of venous blood will be collected. The date and the time of each sample collection will be recorded in the eCRF, with the time of study drug injection (or missed injection, if applicable).

Concentration of AP30663 in the plasma will be determined using 2 analyses as outlined in [Section 11.1.5](#) where concentration-derived PK parameters are also described.

10.1.3 Safety Assessments

10.1.3.1 Adverse Events

Adverse Event Definition

An AE is defined as any untoward medical occurrence in a clinical study patient administered a medicinal product which does not necessarily have a causal relationship with this treatment. An AE can therefore be any unfavourable and unintended sign (including an abnormal laboratory finding), symptom, or disease temporally associated with the use of a medicinal (investigational) product, whether or not it is related to the medicinal (investigational) product. This includes an exacerbation of pre-existing conditions or events, intercurrent illnesses, drug interaction or the significant worsening of the indication under investigation that is not recorded elsewhere in the eCRF under specific efficacy assessments. Anticipated fluctuations of pre-existing conditions, including the disease under study, that do not represent a clinically significant exacerbation or worsening need not be considered AEs.

It is the responsibility of the investigator to document all AEs that occur during the study. AEs will be collected from study assessments including laboratory parameters, physical examination and vital signs and also be elicited by asking the patient a non-leading question, for example, “Have you experienced any new or changed symptoms since we last asked/since your last visit?” AEs should be reported on the appropriate pages of the eCRF.

When collecting AEs, special attention should be paid to AEs related to the risks described in the investigator’s brochure section 7 “Summary of Data and Guidance for the Investigator”.

Assessment of Severity

Each AE will be assigned a category by the investigator as follows:

Mild:	An AE that is easily tolerated by the patient, causes minimal discomfort, and does not interfere with everyday activities.
Moderate:	An AE that is sufficiently discomforting to interfere with normal everyday activities; intervention may be needed.
Severe:	An AE that prevents normal everyday activities; treatment or other intervention usually needed.

If there is a change in severity of an AE, it must be recorded as a separate event.

All local infusion site reactions will be regarded as AEs and reported accordingly. Specific detailed instruction on a standardised assessment of infusion site AEs is provided in the Study Drug Administration Manual.

Assessment of Causality

Every effort will be made by the investigator to assess the relationship of the AE, if any, to the study drug. Causality should be assessed using the categories presented in the following table:

Unrelated:	Clinical event with an incompatible time relationship to study drug administration, and that could be explained by underlying disease or other drugs or chemicals or is incontrovertibly not related to the study drug.
Unlikely:	Clinical event whose time relationship to study drug administration makes a causal connection improbable, but that could plausibly be explained by underlying disease or other drugs or chemicals.
Possible:	Clinical event with a reasonable time relationship to study drug administration, but that could also be explained by concurrent disease or other drugs or chemicals.

Probable:	Clinical event with a reasonable time relationship to study drug administration, and is unlikely to be attributed to concurrent disease or other drugs or chemicals.
Very	Clinical event with plausible time relationship to study drug administration, and that cannot be explained by concurrent disease or other drugs or chemicals.
Likely/Certain:	

Action Taken

The investigator will describe the action taken in the appropriate section of the eCRF, as follows:

- None
- Study drug stopped
- Study drug temporarily interrupted
- Concomitant medication
- Other, specify.

Follow-up of Adverse Events

All investigators should follow patients with AEs until the event is resolved or until, in the opinion of the investigator, the event is stabilised or determined to be chronic. Details of AE resolution must be documented in the eCRF.

Patients should be followed for 30 days after receiving the study drug, and any AEs that occur during this time should be reported according to the procedures outlined below.

Documentation and Reporting of Adverse Events

AEs should be reported and documented in accordance with the procedures outlined below. All AEs occurring during the study must be documented in the relevant eCRF pages. The following data should be documented for each AE:

- Description of the event
- Classification of “serious” or “not serious”
- Severity
- Date of first occurrence and date of resolution (if applicable)
- Action taken
- Causal relationship

- Outcome of event (unknown, recovered, not yet recovered, recovered with sequelae, death [with date and cause reported])

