- n ECG print-outs: within 15 min before infusion start, at 10 min after infusion start, and, in case of conversion from AF, within 1 min after conversion BUT before infusion stop. Diagnosis of AF (defined as absence of discrete P waves and an irregular ventricular rate) to be confirmed based on a 12-lead ECG. On Day 2 the ECG should be completed 24 h +/- 2 hours after infusion start.
- o Continued assessment to start 30 min before infusion. Holter to stop after the PK sampling at 8 h. Telemetry to continue for minimum 8 h after infusion start.
- p Should be done in all patients; mandatory if not done within 6 months (inclusive) before randomisation.
- q Heart rhythm, LV size, LV area, LVEF, atrial area and size as well as other clinically significant finding results to be provided or requested if available.
- r In case of AF persistence at 90 min after start of infusion, a direct-current electrical cardioversion is to be done within 180 min post-infusion start (200 J biphasic synchronised).
- s Recording of any AEs/SAEs will start after the ICF has been signed. From infusion start, special attention should be paid to AEs related to the central nervous system including tremors.

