11.1.4 Safety Variables

The safety endpoints are as follows:

- AEs, ECG variables including significant arrhythmia, physical examination, vital signs, and laboratory variables.
- Changes in QTcF interval data over time.

Methods of Analysis

AEs will be coded using the Medical Dictionary for Regulatory Activities (MedDRA). Summaries will be presented by system organ class (SOC) and preferred term. Treatment-emergent AEs (TEAEs) are defined as any AE occurring or worsening on or

after the first dose of study medication. If a participant experiences the same preferred term multiple times, the event will be counted only once overall and by the greatest severity.

The frequency and incidence of TEAEs will be presented by SOC and preferred term for each treatment group (number and percentage of patients experiencing at least one TEAE per preferred term as well as the number of observed events per preferred term). Separate tables will be presented by severity and by relationship, and for SAEs, related TEAEs, and TEAEs leading to study discontinuation. All AEs will be presented in full in a comprehensive listing including participant number, treatment regimen, severity, seriousness, action taken, outcome, relationship to treatment, onset/stop, and duration. Details of SAEs and AEs leading to withdrawal will be listed separately.

For ECG values, a categorical analysis of outliers (e.g. number of ECGs where QTc >450 ms, and QTc >500 ms and change from baseline of >30 ms and >60 ms) will be computed and summarised.

Changes in QTcF intervals over time will be summarised by means of a shift table. Abnormal findings (“normal”, “abnormal, not clinically significant”, and “abnormal, clinically significant”) will be summarised by the number and percentage within each category, and change from baseline will be summarised within shift tables.

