2.2. Timings of Analyses

The study will be conducted in two parts (Parts 1 and 2): Part 1 of the study is a fixed randomisation placebo-controlled parallel design, and Part 2 will be an adaptive design conducted in one or more further doses of AP30663 vs Placebo.

In Part 1 of the study, up to 36 patients will be randomised in a 1:1 ratio to receive AP30663 at 3 mg/kg or matching placebo. An interim analysis (IA) will be conducted once the randomised patients in Part 1 have completed Day 2 assessments or terminated the study (see section 8.1 of the protocol).

An interim analysis (Part 1) including efficacy, PK/PD, safety and tolerability data will be conducted after all randomised patients have completed Day 2 assessments of the study, in order to determine the starting dose(s) for Part 2 of the study. For further information see section 11. An independent data monitoring committee (DMC) will be convened to review the accumulating unblinded efficacy (including ECG and Holter ECG), PK/PD, safety and tolerability data for the study at the time of the interim analysis.

During Part 2, IAs will occur when 18, 36 and 54 patients have been randomised to open-doses including placebo, and have completed Day 2 assessments or terminated the study.

For Part 2, the DMC will give their recommendations regarding continuation or early termination of the study. Decision rules will be based on the AF conversion rate; however the DMC will also have the option to stop a dose arm (or the study) due to unacceptable safety and tolerability (including but not limited to increase in QTcF interval and number and severity of local injection site reactions).

An unblinded team (unblinded statistician and unblinded programming team) will be responsible for generating and delivering unblinded TFLs to the DMC members. Tables that will be delivered for the interim analysis are detailed in Section 16.

This document is confidential.

3. Study Objectives

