10.3. Adverse Events / Adverse Drug Reactions

AEs will be coded using the Medical Dictionary for Regulatory Activities (MedDRA) version 21.1 or an updated version. Summaries will be presented by system organ class (SOC) and preferred term. Treatment-emergent AEs (TEAEs) are defined as any AE occurring or worsening on or after the first dose of study medication. Partial AE dates will be imputed.

The frequency and incidence of TEAEs will be presented by SOC and preferred term for each treatment group (number and percentage of patients experiencing at least one TEAE per preferred term as well as the number of observed events per preferred term; percentages will be based on the number of patients in the safety set).

The summaries presenting frequency of AEs by SOC and PT will be ordered by overall descending frequency of SOC and then, within a SOC, by overall descending frequency of PT.

Separate tables will be presented by severity and by relationship, and for SAEs, related TEAEs, and TEAEs leading to study discontinuation.

Relationships of 'very likely', 'probable' and 'possible' are to be considered as related to study drug for the summary tables. Relationships of 'unlikely' and 'unrelated' are to be considered not related to study drug.

In case of missing relationships, AEs will be considered as related.

All AEs will be presented in full in a comprehensive listing including patient number, treatment group, severity, seriousness, action taken, outcome, relationship to treatment, onset/stop, and duration. TEAEs will be flagged in the listings.

This document is confidential.

Details of SAEs and AEs leading to withdrawal will be listed separately.

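### Every change in AE severity becomes a new event and nothing rejoins the records, so the SAP's event counts measure severity phases, not episodes

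*Protocol*

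**What the plan says.** - **Recording.** Protocol 10.1.3.1 (Assessment of Severity): "If there is a change in severity of an AE, it must be recorded as a separate event". No direction is specified. The same section treats all local infusion site reactions as AEs.
- **Start of collection.** Protocol 8.1.2, footnote s: "Recording of any AEs/SAEs will start after the ICF has been signed". AEs that begin before infusion will therefore be in the data.
- **Tabulation.** SAP 10.3 asks for the "number and percentage of patients experiencing at least one TEAE per preferred term as well as the number of observed events per preferred term". Protocol 11.1.4 asks for the same.
- **Count-once rule.** Protocol 11.1.4: "If a participant experiences the same preferred term multiple times, the event will be counted only once overall and by the greatest severity". SAP 10.3 does not repeat this sentence, although SAP section 12 declares no changes from the protocol.
- **Treatment emergence.** SAP 10.3: "Treatment-emergent AEs (TEAEs) are defined as any AE occurring or worsening on or after the first dose of study medication".
- **DMC use.** SAP 2.2 lets the DMC stop an arm or the study for unacceptable safety and tolerability, including "number and severity of local injection site reactions".

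Neither document links a severity-change record to its parent event, collapses such records, or says which onset date the new record carries.

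**The concern.** The recording rule and the counting rule do not fit together. One splits an episode at each change in severity; the other counts the resulting records as events. A reader of the table will take the event column as a number of occurrences, when it is a number of severity phases. The listing's duration is affected too, because one episode is cut into shorter pieces.

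The practical stake is the interim reviews. Local reactions are a known effect of the drug (Protocol section 6), and their number is a stated consideration for stopping an arm. The SAP's index of tables marks three AE tables for the DMC: the overall TEAE summary, related TEAEs and serious TEAEs. The maximum-severity table (14.3.1.6), which splitting does not inflate, is not marked. Nor is the AE listing (16.2.7.1), where split records could be recognised. In Part 2 a cohort of 18 randomised 2:1 puts 18 × 2/3 = 12 patients on active drug, or 6 per dose if two doses are open, so a few extra records are visible in a count.

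**Working it through.** The documents state no AE rate or event count, so there is no plan figure to reproduce. The check follows the rules as written.

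**1. Event count.** Let an episode have k severity changes between onset and resolution. Under Protocol 10.1.3.1 it yields 1 + k records. Over E episodes:

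reported events = E × (1 + mean k).

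For example, a reaction going mild, moderate, mild, resolved has k = 2. It gives 3 records and 3 events, in 1 patient.

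To show the range, assume E = 6 episodes and a mean k from 0 to 2. None of these values comes from the documents.

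| Mean changes per episode (assumed) | Factor | Reported events for 6 episodes |
|---|---|---|
| 0 | 1.0 | 6 |
| 0.5 | 1.5 | 9 |
| 1 | 2.0 | 12 |
| 2 | 3.0 | 18 |

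The row for 0 belongs in the range. Protocol section 6 describes the phase 1 infusion site reactions as mild and short-lived, and a reaction that stays mild until it resolves has k = 0.

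**2. What splitting leaves alone.** For an episode that starts after infusion, all 1 + k records sit in one patient under one preferred term. The number and percentage of patients with that term are unchanged. Table 14.3.1.6 shows the patient once, at the highest grade.

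**3. Comparison between arms.** With episode counts E_A (active) and E_P (placebo) and the same mean k in both, the ratio of events is E_A(1 + k) / E_P(1 + k) = E_A / E_P, unchanged. The absolute difference becomes (E_A − E_P)(1 + k), so it grows by the same factor as the counts.

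**4. Treatment emergence.** Take an AE that is moderate before infusion and becomes mild after it. Protocol 10.1.3.1 requires a new record. There are two possible datings:

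- *Onset is the date of the change.* The record occurs after dosing and meets the SAP 10.3 definition. It adds 1 TEAE. It adds a patient to overall incidence only if that patient has no other TEAE, and to the preferred-term row only if the patient has no other TEAE of that term.
- *Onset is the first occurrence.* The AE neither began nor worsened after dosing, so it adds 0.

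Protocol 10.1.3.1 lists the date of first occurrence among the data for each AE but does not say what that means for a split record. SAP 6.3.2 deals only with partial or missing dates. Either dating is compatible with the text.

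**The case against.** The strongest case against is that most of the safety reporting is already protected. Patient counts and percentages stand beside the event counts, the severity table uses the maximum grade, and the final AE listing gives onset, stop and severity for each record, so an analyst could rejoin them. All of that stands, and it confines the defect to the event column and the listed durations. The count-once sentence does not remove it: read as covering event counts, it would contradict the request for observed events in the same section, so it is best read as a rule for patient counts.

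The DMC link has limits. No numeric threshold is attached to the number of reactions, and the text does not say whether events or patients are meant. The layouts of the DMC's AE tables are not given. The DMC Charter and the Study Drug Administration Manual, which holds the standardised infusion-site assessment, are not among the documents and may settle some of this.

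A reader might also infer four stronger things that the documents do not support:

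- *That an improving AE becomes treatment-emergent as a rule.* This depends on an onset date that is left open. It concerns only AEs that start between consent and infusion, a short window, since Protocol 8.1 asks for prompt randomisation and infusion preferably within 12 h of it. Infusion site reactions cannot begin before the infusion, so they are never affected.
- *That each such AE adds a patient to TEAE incidence.* It does so only if the patient has no other TEAE, overall or of that term.
- *That the artefact is biased against active drug.* More reactions on active drug would be a real signal. The recording rule, schedule and blinded assessment are the same in all arms, and nothing shows more severity changes per episode on active.
- *That inflation is at least 1.5-fold.* That follows only if zero changes per episode is excluded, and the phase 1 description gives no reason to exclude it.

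**Conclusion.** The point holds for event counts. Followed as written, the plan reports 1 + k events for an episode with k severity changes. The multiplier is 1.0 to 3.0 for an assumed mean of 0 to 2 changes per episode and may be close to 1; the documents do not allow a better estimate. Patient counts and the maximum-severity table are sound for episodes that start after infusion, and efficacy is untouched.

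The treatment-emergence gap is conditional on how a split record is dated and is confined to AEs that start before infusion. The definition should close it rather than leave it to programming.

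This is worth correcting because the number of local reactions informs arm-stopping decisions in small cohorts, and the SAP does not mark for the DMC the outputs that would reveal the splitting.

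**What to change.** In SAP 10.3:

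1. Derive episodes by joining records of the same patient and preferred term with contiguous dates.
2. Count one event per episode, at its maximum post-infusion severity.
3. Restore the count-once sentence of Protocol 11.1.4, stated as a rule for patient counts.
4. Treat a split record of a pre-infusion AE as treatment-emergent only if its severity exceeds the pre-infusion severity.
5. Apply these rules to the AE tables delivered to the DMC.

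The cost is SAP wording and a small programming derivation, with no new data collection. The downside is that two distinct back-to-back events of the same preferred term could be merged. The protocol's list of AE items names dates, not times, so separate short reactions on the same day are the likeliest case. Keeping the record-level listing lets such cases be checked.
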